4.3 OVERALL STUDY DESIGN

This clinical study will be a multi-center, open label, long-term follow-up study of the patients who were enrolled in the DEFENDO Study.

The DEFENDO Long-Term Follow-up Study will have follow-up with the patients at months 24-30. All patients will be evaluated in the real-world setting post the 6-month off treatment follow up of the DEFENDO Study through 30 months. Patient will be treated per standard of care as determined by the Investigator and will document topical ophthalmic medications. The original DEFENDO Study duration was a total of 34 weeks: a screening period of 2 weeks, followed by enrollment in 8 weeks of OXERVATE™ treatment and an Off-Treatment Follow-Up of 6 months.

After enrollment in the original DEFENDO Study, patients will be invited to enter the DEFENDO Long-Term Follow-up Study (**all standard of care is permitted**). Two (2) additional long-term follow-up visits will occur at 24- and 30-month post-treatment to evaluate long-term clinical outcomes.

[figure not shown]
All patients enrolled in the DEFENDO Study that are not meeting exclusion criteria and are not lost to follow-up will be eligible for the DEFENDO Long-Term Follow-up Study.

During the DEFENDO Long-Term Follow-up Study, the patients may be treated at the physician's discretion. Any concomitant treatment must be documented. If warranted for patient safety, the Investigator may elect to see the patient at an Unscheduled Visit(s) to evaluate the patient.

Corneal healing will be graded at a Central Reading Center per the Reading Center Charter.

Figure 1 Study Schematic

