8 ENDPOINTS

8.1 STUDY ENDPOINTS

- Percentage of patients who have corneal epithelial healing at 24 months and 30 months of the long-term follow-up.
 - Percentage of patients who had corneal epithelial healing at week-8 in the DEFENDO Study, who maintain healing at month 24 and month 30 of the long-term follow-up.
 - Percentage of patients who did not have corneal epithelial healing at week-8 in the DEFENDO Study who have a healed corneal epithelium at month 24 and month 30 of the long-term follow-up.
- Percentage of patients who achieved an improvement in corneal sensitivity at 24 months and 30 months of the long-term follow-up.
 - Percentage of patients who achieved an improvement in corneal sensitivity at week-8 in the DEFENDO Study who still have improvement in corneal sensitivity at 24 months and 30 months of the long-term follow-up.
 - Percentage of patients who did not achieve an improvement in corneal sensitivity in the DEFENDO Study who have improvement in corneal sensitivity at 24 months and 30 months of the long-term follow-up.
- Change from the Baseline Visit in the DEFENDO Study in Schirmer I scores at 24 months and 30 months of the long-term follow-up.
- Change from the Baseline Visit in the DEFENDO Study in TFBUT at 24 months and 30 months of the long-term follow-up.
- Change from the Baseline Visit in the DEFENDO Study in BCDVA at 24 months and 30 months of the long-term follow-up.
- Percentage of patients who achieved a 15-letter improvement in BCDVA at 24 months and 30 months compared to the Baseline Visit and Week 8 of the DEFENDO Study.
- Change from the Baseline Visit in the DEFENDO Study in quality of life as measured with the IDEEL at 24 months and 30 months of the long-term follow-up.
- Change from the Baseline Visit in the DEFENDO Study in quality of life as measured with the EQ-5D-5L at 24 months and 30 months of the long-term follow-up.

CCI

CCI

CCI

CCI

CCI

[figure not shown]
CCI

CCI

CCI

CCI

C

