2.2 Study Period, Visit, and Day

The study period, visit, and day will be integrated across the NGF0120 and NGF0122 studies, and will consist of screening, baseline (Day -1), treatment (Week 2, Week 4, Week 8), follow-up (Week 32), extended follow-up Month 24 or Week 96, and extended follow-up Month 30 or Week 120.

A reference date refers to the date of the first study product administration in the study NGF0120. All safety and efficacy assessments at all visits will be assigned a day relative to this date. The relative day will be defined as:

- visit date – reference date + 1 for visits on or after the reference date, and
- visit date – reference date, for visits before the reference date.

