5 ANALYSIS OF EFFICACY

All efficacy analyses will be considered exploratory and performed based on the observed cases in the FAS population. No missing data imputation will be considered.

For continuous efficacy endpoints, descriptive statistics of the observed and change from baseline will be tabulated by visit where that endpoint is assessed. Where appropriate, the asymptotic 95% confidence intervals of mean change from baseline will be presented as well as p values from one-sample t-test and Wilcoxon signed rank test (depending on the distribution of the data) to compare the observed values vs baseline.

For responder/categorical efficacy endpoints, analyses will include percentage of responders/categorized results, and associated exact (Clopper-Pearson) 95% confidence intervals where appropriate as well as p values from a binomial test to assess that responder rates are greater than zero.

- Percentage of patients who had corneal epithelial healing at Week 8 in the DEFENDO Study, who maintain healing at Month 24 and Month 30 of the long-term follow-up

The patients who had corneal epithelial healing at Week 8 and maintain healing at Month 24 and Month 30 will be summarized as a binary goal attainment variable (Yes/No) based on the subset of patients who achieved corneal epithelial healing at Week 8, as determined by the CRC.

- Percentage of patients who did not have corneal epithelial healing at Week 8 in the DEFENDO Study who have a healed corneal epithelium at Month 24 and Month 30 of the long-term follow-up

The patients who did not have corneal epithelial healing at Week 8 and who have corneal epithelial healing at Month 24 and Month 30 will be summarized as a binary goal attainment variable (Yes/No) based on the subset of patients who did not have corneal epithelial healing at Week 8, as determined by the CRC.

- Percentage of patients who achieved an improvement in corneal sensitivity at Week 8 in the DEFENDO Study who still have improvement in corneal sensitivity at Month 24 and Month 30 of the long-term follow-up

The improvement in corneal sensitivity is defined as change from baseline > 0 (cm) of the study eye. The patients who achieved an improvement in corneal sensitivity at Week 8 and still have improvement in corneal sensitivity at Month 24 and Month 30 will be summarized as a binary goal attainment variable (Yes/No) based on the subset of patients who achieved an improvement in corneal sensitivity at Week 8.

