Appendix 2 Tables, Listing, and Figures**List of tables**

Table Number	Table Title	Analysis Population
14.1.1	Analysis Populations	
14.1.2	Subject Disposition	Full Analysis Set
14.1.3	Visit Participation	Full Analysis Set
14.1.4	Demographics	Full Analysis Set
14.1.5.1	Medical History	Full Analysis Set
14.1.5.2	Ocular History	Full Analysis Set
CCI		
14.1.6.3	Non-ocular Medications during Extended Follow-up	Full Analysis Set
14.2.1.1	Percentage of Patients who Achieved Epithelial Healing at Week 8 and Had Healed during Extended Follow-up	Full Analysis Set
14.2.1.2	Percentage of Patients who Did Not Achieve Epithelial Healing at Week 8 and Had Healing during Extended Follow-up	Full Analysis Set
14.2.2.1	Corneal Sensitivity Changes from Baseline and Week 8 during Extended Follow-up	Full Analysis Set
14.2.2.2	Percentage of Patients Who Improved in Corneal Sensitivity from Baseline to Week 8 and Still Had Improvement during Extended Follow-up	Full Analysis Set
14.2.2.3	Percentage of Patients Who Did Not Improve from Baseline in Corneal Sensitivity at Week 8 and Had Improvement during Extended Follow-up	Full Analysis Set
14.2.3	Schirmer I Change from Baseline and Week 8 during Extended Follow-up	Full Analysis Set
14.2.4	TFBUT Change from Baseline and Week 8 during Extended Follow-up	Full Analysis Set
14.2.5.1	BCDVA Change from Baseline and Week 8 during Extended Follow-up	Full Analysis Set
14.2.5.2	Percentage of Patients Achieved a 15- letter Gain from Baseline in BCDVA during Extended Follow-up	Full Analysis Set
14.2.5.3	Percentage of Patients Achieved a 15- letter Gain from Week 8 in BCDVA during Extended Follow-up	Full Analysis Set
14.2.6	IDEEL Change from Baseline and Week 8 during Extended Follow-up	Full Analysis Set
14.2.7	EQ-5D-5L Change from Baseline and Week 8 during Extended Follow-up	Full Analysis Set
CCI		
14.3.1.1	Summary of Adverse Events during Extended Follow-up	Full Analysis Set
14.3.1.2	Frequency of Adverse Events by System Organ Class and Preferred Term during Extended Follow-up	Full Analysis Set
14.3.1.3	Frequency of Adverse Events by System Organ Class and Preferred Term and by Maximum Severity during Extended Follow-up	Full Analysis Set
14.3.1.4	Frequency of Adverse Events by System Organ Class and Preferred Term and by Closest Relatedness during Extended Follow-up	Full Analysis Set

Table Number	Table Title	Analysis Population
14.3.1.5	Adverse Event - MedDRA Glossary	Full Analysis Set

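### The SAP's 'maintain healing' rate is late-visit status among Week 8 healers; no visible rule uses Week 32, so it is only an upper limit on sustained healing

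*SAP*

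**What the plan says.** Protocol 8.1 lists, under the overall healing percentage, the share of patients healed at Week 8 "who maintain healing at month 24 and month 30 of the long-term follow-up". SAP section 5 repeats this: "The patients who had corneal epithelial healing at Week 8 and maintain healing at Month 24 and Month 30" are to be "summarized as a binary goal attainment variable (Yes/No) based on the subset of patients who achieved corneal epithelial healing at Week 8", with Week 8 healing determined by the central reading center. Neither document says what *maintain* requires between Week 8 and the late visits.

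SAP 2.2 gives the integrated visit sequence as "treatment (Week 2, Week 4, Week 8), follow-up (Week 32), extended follow-up Month 24 or Week 96", followed by Month 30. Week 8 is thus a treatment visit and Week 32 is a follow-up visit. Protocol 4.3 describes the parent study as a 2-week screening period "followed by enrollment in 8 weeks of OXERVATE™ treatment and an Off-Treatment Follow-Up of 6 months", 34 weeks in all.

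SAP 2.8 summarises categorical endpoints at each scheduled visit. SAP 1.3.3.1 describes central reading of images from Months 24 and 30, and section 5 adds central determination at Week 8. The planned output, Table 14.2.1.1 in SAP Appendix 2, is titled "Percentage of Patients who Achieved Epithelial Healing at Week 8 and Had Healed during Extended Follow-up".

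SAP section 5 has a parallel endpoint for patients whose corneal sensitivity improved at Week 8 and is still improved at the late visits.

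**The concern.** Maintenance suggests a state that lasted. What is scored is status at one or two late visits, given status at the end of dosing. A patient healed at Week 8, graded unhealed at Week 32 and healed again at Month 24 would be a success at Month 24. Protocol 6.2 allows standard of care between visits, including the commercial product, so loss of healing followed by re-healing is possible. Fluctuating staining could produce the same pattern.

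Long-term efficacy in terms of healing is a primary objective. With one arm and no control, each patient's own course carries the interpretation. If known unhealed findings in between are left out, the error runs one way: the rate can only look better than the rate of healing that persisted through the assessed visits.

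**Working it through.** The plan has no figure to reproduce. The 37 patients are the parent study's enrolment, and no healing rate or count is stated. The check is therefore a reading of the rules, followed by an illustration on assumed counts.

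**1. Position of Week 32.** Total duration less screening is 34 − 2 = 32 weeks from the start of treatment, and 32 − 8 = 24 weeks off treatment. Week 32 is the end of the off-treatment period.

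**2. Is Week 32 used?** In the visible text of SAP section 5 and the Appendix 2 table list, efficacy comparisons are with baseline or Week 8, at Months 24 and 30. No rule makes a patient a non-maintainer because of a Week 32 finding. This holds however Months 24 and 30 are combined.

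**3. Is Month 24 used in the Month 30 result?** Three readings are possible:
- *Separate visits.* SAP 2.8 summarises by visit, and the change endpoints in section 5 use the same pair of visits where separate results are plainly meant. Month 30 status then ignores Month 24.
- *Joint.* One Yes/No variable requires healing at both visits. The wording of the endpoint does not exclude this, and a patient unhealed at Month 24 would fail.
- *Either visit.* The title of Table 14.2.1.1 could be read so.

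The first is favoured, but the text does not settle it.

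**4. Direction.** Among Week 8 healers observed at a late visit, those healed at every assessed visit are a subset of those healed at that visit. Hence sustained rate ≤ reported rate.

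**5. How far apart they can be.** If a proportion p is healed at each of k visits, the share healed at all k lies between max(0, kp − (k − 1)) and p.

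| Assumed p | Month 24 and Month 30 (k = 2) | Week 32, Month 24 and Month 30 (k = 3) |
|---|---|---|
| 70% | 40% to 70% | 10% to 70% |
| 80% | 60% to 80% | 40% to 80% |
| 90% | 80% to 90% | 70% to 90% |

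**6. Size per patient.** Let m be the Week 8 healers observed at Month 30, x those healed at Month 30, and j those among the x who were seen unhealed in between. The reported rate is x/m and the sustained rate is (x − j)/m. All counts are assumed, with x/m = 80%.

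| m | x | j = 0 | j = 1 | j = 2 | j = 4 |
|---|---|---|---|---|---|
| 15 | 12 | 80.0% | 73.3% | 66.7% | 53.3% |
| 20 | 16 | 80.0% | 75.0% | 70.0% | 60.0% |
| 25 | 20 | 80.0% | 76.0% | 72.0% | 64.0% |

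For m = 20 the exact (Clopper-Pearson) 95% intervals are 56.3 to 94.3, 50.9 to 91.3, 45.7 to 88.1 and 36.1 to 80.9. Each patient moves the rate by 1/m: 1/25 = 4.0 points to 1/15 = 6.7 points.

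**7. Missing late visits.** SAP 2.10 uses observed cases and drops missing values from the denominator. A Week 8 healer unhealed at Month 24 and absent at Month 30 therefore leaves the Month 30 rate, although healing was already seen to be lost. With 16 of 20 healed at Month 30 and one such patient, the reported figure is 16/20 = 80.0%; counting the observed failure gives 16/21 = 76.2%.

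**The case against.** Much of the case on the other side stands, and it limits the point.

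- A reader might infer that the SAP definitely counts a patient unhealed at Month 24 as maintained at Month 30. It does not say so. Under the joint reading that patient fails. The defect there is ambiguity, not an explicit rule.
- A reader might infer that the integrated data already show relapses at Week 32. SAP 2.2 lists visits, not assessments. Nothing visible says that healing was graded at Week 32, and SAP 1.4 integrates parent data only as applicable. Redactions in the endpoints and table list also mean that non-use of Week 32 can be asserted only for the visible text.
- A reader might conclude that the endpoint should be replaced by healing at every visit. That would let one transient or misgraded finding count as permanent failure. Patients with fewer assessed visits would also have fewer chances to fail, and the SAP 2.5 analysis set admits patients with only one late visit.
- A reader might take durability off treatment to be the stated objective. The stated objective is long-term safety and efficacy, with standard of care permitted.
- The title of Table 14.2.1.1 already avoids the word *maintain*, and the endpoint names its time points openly.
- Still having improved sensitivity need not mean improvement without a break, and mean changes are reported as well. The parallel point there is weaker.

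SAP 2.9 calls the study exploratory. That removes any question of type I error, but a descriptive percentage still needs a label that matches what it measures.

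**Conclusion.** The concern holds in a limited form. On any reading, the visible rules let a Week 8 healer who was unhealed at Week 32 count as maintained at Month 24. On the likelier, by-visit reading, the Month 30 result also ignores Month 24. The reported percentage is thus an upper limit on sustained healing among patients observed at that visit.

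The size of the gap is unknown. The figures of 4 to 6.7 points per patient rest on an assumed 15 to 25 Week 8 healers, and the number of patients with this pattern could be zero. With at most 37 patients, one or two would visibly change the result. The documents do not establish that any relapse was recorded or that Week 32 healing grades exist. The issue affects what can be claimed about lasting healing, not sample size or error rates.

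**What to change.** 1. State in SAP section 5 whether Months 24 and 30 are two separate results or one joint variable, and align the title of Table 14.2.1.1.
2. Keep the current rate, labelled *healed at Month 24/30 among Week 8 healers*.
3. Add a supplementary rate, *healed at every assessed visit since Week 8*. Any observed unhealed visit counts as not sustained, even if a later visit is missing. Report how many patients lack an intermediate assessment.
4. Add a status table over Week 8, Week 32, Month 24 and Month 30.
5. First confirm whether healing was graded at Week 32. Use that visit only if it was. Show any investigator-only grade separately and labelled, not mixed with central grades. If there is no grade, items 1 to 3 still apply with Month 24 as the intermediate visit.
6. Optionally, add a parallel row for corneal sensitivity.

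The cost is SAP wording, a few table rows and one table, with no new data collection. The sustained rate may be less favourable, and it is sensitive to transient staining and misgrading. For that reason it stands beside the point-status rate and does not replace it.

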The phase IV DEFENDO Study involving OXERVATE™ 0.002% (20 mcg/mL) cenegermin-bk bj ophthalmic solution has since been undertaken to provide additional efficacy and safety information related to OXERVATE™ 0.002% (20 mcg/mL) cenegermin-bk bj ophthalmic solution. This study enrolled 37 Stage 1 NK patients who were treated with OXERVATE™ 0.002% (20 mcg/mL) cenegermin-bk bj ophthalmic solution 6 times per day at 2-hour intervals for eight weeks. The DEFENDO Study reported 33 probable and 20 possible adverse events (AEs) that were determined to be related to the Study Product; however, only 3 patients discontinued the study because of the AEs they experienced. While these data are still being analyzed, the DEFENDO Long-Term Follow-up Study is a continuation of the DEFENDO Study, which aims to understanding the efficacy and safety OXERVATE™.

0.002% (20 mcg/mL) cenegeamin-bk bj ophthalmic solution at 24 and 30 months after the completion of the DEFENDO Study.

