5.1 INCLUSION CRITERIA

To be eligible for inclusion into this study, each patient must fulfil the following inclusion criteria:

1. Previously enrolled in the DEFENDO Study.
2. Satisfy all Informed Consent requirements.
 - The patient and/or his/her legal representative has read, signed, and dated the IRB approved Informed Consent document before any study-related procedures are performed.
3. Must have the ability and willingness to comply with study procedures.

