10.3.2 Analysis of efficacy variables

Efficacy endpoints will be analyzed at each available time point by appropriate inferential tests versus baseline and/or week 8. All tests will be descriptive in nature, no formal hypothesis test will be conducted.

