1.1 Study Objectives

Primary Objective

The primary objectives are to evaluate the long-term safety and efficacy (corneal epithelial healing) of OXERVATE™ 0.002% (20 mcg/mL) cenegermin-bk bj ophthalmic solution in Stage 1 Neurotrophic Keratitis (NK) patients who enrolled in the DEFENDO Study.

Secondary Objective

The secondary objectives are to evaluate the long-term efficacy of OXERVATE™ 0.002% (20 mcg/mL) cenegermin-bk bj ophthalmic solution in terms of Corneal Sensitivity, Schirmer I Test, Tear Film Break Up Time (TFBUT), Best Corrected Distance Visual Acuity (BCDVA), and Quality of Life at 24 and 30 months.

CCI

CCI

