- Percentage of patients who did not achieve an improvement in corneal sensitivity at Week 8 in the DEFENDO Study who have improvement in corneal sensitivity at Month 24 and Month 30 of the long-term follow-up

The patients who did not achieve an improvement in corneal sensitivity at Week 8 and who have improvement in corneal sensitivity at Month 24 and Month 30 will be summarized as a binary goal attainment variable (Yes/No) based on the subset of patients who did not achieve an improvement in corneal sensitivity at Week 8.

- Mean change in corneal sensitivity from baseline and Week 8 at Month 24 and Month 30

The corneal sensitivity (cm) in the NEI zone of the study eye as measured by the Cochet-Bonnet aesthesiometer will be summarized as a continuous variable.

- Schirmer I change from baseline and Week 8 to Month 24 and Month 30

The Schirmer tear test result (mm) in the study eye will be summarized as a continuous variable.

- TFBUT change from baseline and Week 8 to Month 24 and Month 30

The average TFBUT result (sec) of two repeat measurements in the study eye will be summarized as a continuous variable.

- Mean change in BCDVA from baseline and Week 8 to Month 24 and Month 30

The logMAR visual acuity score in the study eye will be summarized as a continuous variable.

- Percentage of patients that achieve a 15-letter gain from baseline and Week 8 in BCDVA at Month 24 and Month 30

The patients that achieve a 15-letter gain in BCDVA will be determined based on $\text{logMAR} - \text{Baseline logMAR} \leq -0.3$. It will be analyzed using a binary goal attainment variable (Yes/No).

- IDEEL change from baseline and Week 8 at Month 24 and Month 30

Subscores will be derived for the following modules and will be calculated only if at least 50% of the items of the dimension are completed; otherwise, the scores are missing.

Module 1:

Dry eye impact on daily life (27 questions) comprising 3 QoL domains: 1.a “Daily activities limitations”, 1.b “Emotional wellbeing” and 1.c “Work limitations”. 26 questions will be considered as part of one of these 3 domains. Question 22 will not be considered part of a domain.

1.a: Daily Activities

Daily activities section	Used in calculation of domain score?
1. Doing close work in the morning or afternoon (such as crossword puzzles, reading, looking at a computer, and/or sewing)	Yes
2. Doing close work in the evening or at night	Yes
3. Driving	Yes

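### The protocol lists overall healing and overall sensitivity-improvement rates at Months 24 and 30, but the SAP itemises only the Week 8 subset rates; its responder test against zero is uninformative

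*SAP*

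**What the plan says.** Protocol 8.1 gives two responder endpoints for all patients: "Percentage of patients who have corneal epithelial healing at 24 months and 30 months of the long-term follow-up" and "Percentage of patients who achieved an improvement in corneal sensitivity at 24 months and 30 months of the long-term follow-up". Two rates split by Week 8 status sit under each. The synopsis has the same structure.

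SAP Section 5 defines the four split rates and neither overall rate. The maintained-healing rate is "based on the subset of patients who achieved corneal epithelial healing at Week 8, as determined by the CRC"; at the other end, later sensitivity improvement is "based on the subset of patients who did not achieve an improvement in corneal sensitivity at Week 8". The table list in SAP Appendix 2 matches Section 5. SAP Section 9 states that nothing departs from the protocol.

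On testing, Protocol 10.3.2 says: "Efficacy endpoints will be analyzed at each available time point by appropriate inferential tests versus baseline and/or week 8". For responder endpoints, SAP Section 5 plans percentages, Clopper-Pearson 95% intervals where appropriate, and a binomial test that the rate exceeds zero. SAP 2.9 and Section 5 call all efficacy analyses exploratory.

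**The concern.** SAP 1.1 names corneal epithelial healing as the efficacy part of the primary objective, in patients who enrolled in the parent study, with no condition on Week 8 status. The most direct summary is the share of followed patients who are healed at Month 24 and at Month 30. Programmed as itemised, the plan yields two conditional rates with different denominators and leaves the reader to combine them. Sensitivity is a secondary objective and already has an overall mean change, so that omission matters less.

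The responder p values raise a separate problem. A test that a rate exceeds zero shows only that at least one responder exists. Beside a maintained-healing rate it could be read as evidence of durability, which it does not measure.

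**Working it through.** **Step 1. Compare the lists.** The plan has no power calculation to reproduce: the sample is however many of the 37 parent-study patients roll over.

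| Protocol 8.1 endpoint | SAP Section 5 | SAP Appendix 2 |
|---|---|---|
| Healed, all patients | not itemised | no table |
| Healed at Week 8, still healed | yes | 14.2.1.1 |
| Not healed at Week 8, later healed | yes | 14.2.1.2 |
| Sensitivity improved, all patients | not itemised | no table (14.2.2.1 is mean change) |
| Improved earlier, still improved | yes | 14.2.2.2 |
| Not improved earlier, later improved | yes | 14.2.2.3 |

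**Step 2. Check redaction.** In the table list, the blacked-out blocks fall before 14.1.6.3 and after 14.2.7. In Section 5 the blacked-out text follows EQ-5D-5L. Numbering within 14.2.1.x and 14.2.2.x is unbroken, so redaction does not explain the gap.

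**Step 3. Rebuild the overall rate.** The documents give no Week 8 counts, so these are assumed. Take 30 patients with both readings: 22 healed at Week 8, of whom 17 remain healed, and 8 not healed, of whom 4 heal later. Clopper-Pearson limits are the 2.5% point of Beta(x, n-x+1) and the 97.5% point of Beta(x+1, n-x).

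- Healed at Week 8: 17/22 = 77.3% (54.6% to 92.2%).
- Not healed at Week 8: 4/8 = 50.0% (15.7% to 84.3%).
- Overall: (17+4)/(22+8) = 21/30 = 70.0% (50.6% to 85.3%).

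Only the first two lines are itemised outputs.

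**Step 4. Patients without a Week 8 result.** They would be in neither subset table. As a separate assumed case, let 30 patients have a follow-up reading, 21 of them healed, and let k lack a Week 8 result. The rebuilt rate then lies between (21-k)/(30-k) and 21/(30-k), against a true 70.0%.

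| k | Lowest | Highest |
|---|---|---|
| 0 | 21/30 = 70.0% | 70.0% |
| 1 | 20/29 = 69.0% | 21/29 = 72.4% |
| 2 | 19/28 = 67.9% | 21/28 = 75.0% |
| 3 | 18/27 = 66.7% | 21/27 = 77.8% |

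The ceiling of 3 is an assumption, taken from Protocol 3.2: "only 3 patients discontinued the study because of the AEs they experienced". When they stopped is not stated.

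**Step 5. The test against zero.** With null rate 0, P(X >= 1) = 1 - (1-0)^n = 0 and P(X >= 0) = 1, for every n. The exact p value is therefore 0 with any responder and 1 with none. With a true rate of only 5%, the chance of rejecting is 1 - 0.95^n: 0.40 at n = 10, 0.64 at n = 20 and 0.85 at n = 37.

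The SAP does not say that the test is exact. The usual score version has null standard error sqrt(0 x 1/n) = 0 and is undefined. A Wald version for 1/20 gives z = 0.05/sqrt(0.05 x 0.95/20) = 1.026, one-sided p = 0.152. The planned exact interval for 1/20, 0.1% to 24.9%, says more than either.

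**Step 6. Is zero ever the right reference?**

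- Sensitivity improvement is defined as change from baseline above 0 cm, so zero is the baseline reference. The 15-letter gains are likewise measured from their own reference visit.
- In the not-healed and not-improved subsets, zero is the Week 8 rate by construction.
- In the healed-at-Week-8 subset the Week 8 rate is 100% by construction. The question there is how much healing was lost, and zero is the wrong reference.

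**Step 7. A comparison that can discriminate.** In the Step 3 example Week 8 healing is 22/30 = 73.3%, with 22-17 = 5 lost and 4 gained. Exact McNemar, two-sided binomial(9, 0.5), gives p = 1.00. With 8 lost and 1 gained, p = 2 x (1+9)/512 = 0.039.

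**The case against.** A good part of the other side stands.

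- **A method already exists.** SAP Section 5 has a general responder rule (percentage with exact interval), and SAP Section 1 says to read the SAP with the protocol. The rule could cover the overall rates, and the mock shells, which are a separate document, may contain them. This stands as mitigation, but the rule names no overall endpoint and no table carries one.
- **The rate is recoverable.** SAP 2.8 requires counts, and Listings 16.2.6.1 and 16.2.6.2 cover the underlying results. This stands for every patient with a Week 8 result.
- **There may be no patient without one.** Eligibility asks only for "Previously enrolled in the DEFENDO Study", but Protocol 3.3 speaks of completers, Protocol 5 leaves out patients lost to follow-up, and the closest-visit rule in SAP 2.4 may fill gaps. The number is unknown and possibly none. Even at k = 3 the distortion is at most 7.8 points, inside an interval about 35 points wide.
- **Protocol 10.3.2 is loosely worded.** It asks for suitable tests against baseline, Week 8 or both. As Step 6 shows, zero is nominally such a reference for several endpoints. A reader might infer that the responder endpoints have no comparison with baseline or Week 8, or that the protocol requires a McNemar test. The documents support neither reading.

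A reader might also infer that the sponsor chose to drop the overall endpoints. An incomplete list explains the text equally well, and nothing in the documents decides between the two.

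**Conclusion.** The point holds in a limited form. Two overall responder rates listed in Protocol 8.1 are not itemised in SAP Section 5 or the visible table list, and SAP Section 9 does not say so. It matters more for healing, the efficacy part of the primary objective, than for sensitivity. The rates are not lost: they follow by addition for patients with a Week 8 result, and the remaining error is zero if all have one.

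The zero test is uninformative wherever it is used, and for maintained healing it also has the wrong reference. It would go too far to say that it breaches Protocol 10.3.2 across all responder endpoints.

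Severity is minor: completeness and traceability. All analyses are exploratory and no decision depends on this. The comparison of the lists rests on the visible text alone. The rates and intervals in Steps 3, 4 and 7 rest on assumed counts; the behaviour of the exact zero test does not.

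**What to change.** 1. Add two overall tables to SAP Section 5 and Appendix 2, at each of Month 24 and Month 30 and regardless of Week 8 status: healing as graded by the central reading center, and sensitivity change from baseline above 0. Base each on full-analysis-set patients with data at that visit, and give n/N, the Clopper-Pearson 95% interval and the number without a Week 8 result. These need to be separate tables: a total row inside a subset table gives no overall rate, and summing the subsets omits anyone without a Week 8 result. If the overall rates are not wanted, declare the omission in SAP Section 9.
2. Remove the test against zero from all responder tables, report responder rates with exact intervals only, and record this in SAP Section 9.
3. Optionally, add a descriptive exact McNemar test against Week 8 for the two overall rates, in patients with both readings.

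Cost: a short SAP edit, two added tables from data already collected, and deletion of the zero-test p values from the existing responder tables.
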